#### 4.3 Rationale for Inclusion/Exclusion Criteria

In order to establish the preliminary efficacy of Dysport in this dose escalation and dose expansion study, a subset of vulvodynia subjects suffering from provoked vestibular pain is selected. It is hypothesised that pelvic floor muscle hypertonicity underpins the posterior vestibular pain experienced and consequently, these subjects are likely to respond to treatment with Dysport. Hence, the inclusion and exclusion criteria for this study have been tailored to ensure enrolment of female subjects with a confirmed diagnosis of PVD based on the three established criteria as per Pukall 2007 [21]: self-report of superficially-located pain during sexual intercourse; a lack of physical findings (e.g. infections) to explain the pain or the persistence of pain after conditions believed to be related to the pain have been treated; and a positive response (i.e. pain) during the cotton-swab test. This will also help target a homogenous subject population and limit intersubject variability.

#### 4.4 Subject Withdrawal Criteria and Procedures

In accordance with the Declaration of Helsinki (in accordance with the applicable country's acceptance), each subject is free to withdraw from the study at any time.

The investigator and/or sponsor can withdraw a subject at any time for any reason (e.g. protocol violation).

The investigator also has the right to withdraw a subject from the study for reasons including:

- If required by the DRC due to reasons described in Section 3.1.1.2
- Any AE that jeopardises the safety of the subjects
- Other reasons concerning the health or wellbeing of the subject
- In the event of concurrent illness, based on the benefit risk for the subject as assessed by the investigator (see concomitant medications not permitted in Section 6.3)
- Pregnancy (see Section 8.1.7)
- Lack of cooperation in completing the study visits or schedules or study assessments
- Study is stopped or discontinued (See Section 3.9 for further details)
- Death (see Section 8.1.8)
- Any other reason as judged by the investigator to be in the best interest of the subject.

If a subject decides to withdraw from the study after administration of IMP, or should the investigator decide to withdraw the subject, all efforts will be made to complete and report the observations at least 12 weeks after the last dose or up to the time of withdrawal as thoroughly as possible. A complete assessment should be made and final evaluations be done at the time of the subject's withdrawal as described in Section 5.2.4 with an explanation given of why the subject is withdrawing or being withdrawn from the study.

The reason for and date of withdrawal from the study must be recorded on the eCRF. If a subject withdraws consent, every attempt will be made to determine the reason. If the reason for withdrawal is an AE or a clinically significant laboratory test abnormality, monitoring will continue until the event has resolved or stabilised, until the subject is referred to the care of a local health care professional, or until a determination of a cause unrelated to the IMP or study procedure is made. The specific AE or test result(s) must be recorded on the eCRF. All evaluations should be performed, according to the protocol, on the last day the subject receives IMP, or as soon as possible thereafter.

## 5 STUDY PROCEDURES

### 5.1 Study Schedule

The schedule of procedures and assessments during the study for the double-blind treatment period is summarised in [Table 2](#) and for the open-label treatment period in [Table 3](#).

Subjects enrolled prior to implementation of Version 3.0 (dated 04 November 2018), i.e. subjects included in Cohort 1, will continue to follow the study assessments and procedures as per the protocol Version 2.0 (dated 15 May 2018).

If the COVID-19 pandemic prevents subjects from coming to the site, subjects can have their study visit assessments performed remotely as judged appropriate by the investigator; the medical monitor/sponsor must be informed before implementing this. In such a case, the investigator will perform a telemedicine visit and will make every effort, where applicable, to contact the subject's general practitioner or equivalent to ensure all important medical information and safety event(s) occurring since the last visit are collected. Guidance on how to collect protocol-planned assessments will be provided to the investigator in a separate document. Such document will be filed in the Trial Master File (TMF). IECs/IRBs will be notified of the changes as applicable locally. Of note, as the adapted visit deviates from the regular protocol plan, the changes will be recorded as protocol deviations related to COVID-19.

Table 2 Study Procedures and Assessments – Double-Blind Treatment Period

Study Procedures and Assessments	Pretreatment		Double-Blind Treatment Period Cycle 1							End of Cycle 1/ EOS or EWD [b]	
	V1	V2	V3	V4	V5 [a]	Additional Visits [a]					
						V6	V7	V8			
Visit Day/Week No.	Screening (Day -14) [m]	Baseline (Day 1)	Week 2 (Day 15)	Week 6 (Day 43)	Week 12 (Day 85)	Week 18 (Day 127)	Week 24 (Day 169)	Week 30 (Day 211)	Week 36 (Day 253)		
Type of visit	Clinic	Clinic	Telephone	Clinic	Clinic	Clinic	Clinic	Clinic	Clinic		
Visit Window	-14 days/ +3 days		±3 days	±5 days	+14 days	±14 days	±14 days	±14 days	±14 days	±14 days	
Informed consent [c]	X										
Inclusion/exclusion criteria	X	X									
Demographic data	X										
Height, weight, BP, HR	X										
Physical examination	X										
Significant medical/ surgical/ vulvodynia history	X										
Prior/concomitant medications and non-drug therapies (incl. BTX, sex therapy, physiotherapy, pain rescue medication)*	X	X	X	X	X	X	X	X	X		
Adverse events*	X	X	X	X	X	X	X	X	X		
Urine pregnancy test	X									X	
Urine test for illicit drugs	X			X						X	
PCS	X										
PGI-S [e]*	X	X		X	X	X	X	X	X		
PGI-C [e]*				X	X	X	X	X	X		
eDiary mVPAQ pain subscale [e]*	X	X		X	X	X	X	X	X		
eDiary mVPAQ life interference subscale [e]*	X	X		X	X	X	X	X	X		
eDiary mFSFI pain domain [e]	X	X		X	X	X	X	X	X		
mVPAQ subscales (except pain and life interference) [f]*	X	X		X	X		X			X	
mFSFI domains (except pain) [f]*	X	X		X	X	X	X	X	X		
eDiary relationship/partner status [g]*	X	X		X	X	X	X	X	X		
eDiary dilator insertion [k]*	X	X		X	X	X	X	X	X		
PHQ-9*		X			X					X	

Study Procedures and Assessments	Pretreatment		Double-Blind Treatment Period Cycle 1							End of Cycle 1/ EOS or EWD [b]	
	V1	V2	V3	V4	V5 [a]	Additional Visits [a]					
						V6	V7	V8			
Visit Day/Week No.	Screening (Day -14) [m]	Baseline (Day 1)	Week 2 (Day 15)	Week 6 (Day 43)	Week 12 (Day 85)	Week 18 (Day 127)	Week 24 (Day 169)	Week 30 (Day 211)	Week 36 (Day 253)		
Type of visit	Clinic	Clinic	Telephone	Clinic	Clinic	Clinic	Clinic	Clinic	Clinic		
Visit Window	-14 days/ +3 days		±3 days	±5 days	+14 days	±14 days	±14 days	±14 days	±14 days		
SF-36*		X			X					X	
eDiary intercourse details [h]*	X	X		X	X	X	X	X	X		
Q-tip test	X										
Dilator test	X	X		X	X	X	X	X	X		
Vaginal swab	X										
Measurement of pelvic floor pressure [n]		X		X	X	X	X	X	X		
CGI				X	X	X	X	X	X		
Clinical laboratory tests (nonfasting biochemistry, haematology, FSH [i])**	X				X					X [d]	
Blood sample for antibodies**	X									X [d]	
Randomisation		X									
Study drug administration			X [j]								
Assessment for retreatment					X	X	X	X			
Subject Interviews				X [l]							

BP=blood pressure, BTX=botulinum toxin, CGI=clinical global impression, EOS=end of study, EWD=early withdrawal, FSH=follicle stimulating hormone, HR=heart rate, ICF=informed consent form, mFSFI=modified female sexual function index, incl.=inclusive, mVPAQ=modified vulvar pain assessment questionnaire, NRS=numeric rating scale, PGI=patient global impression, PHQ-9=patient health questionnaire, SF-36=36-item short form survey, V=visit.

- a From Week 12 onwards, if no retreatment is required, the subject will attend Additional Visits every 6 weeks until retreatment is required or Week 36 (EOS) is reached. When subject is eligible and all retreatment criteria are fulfilled at any visit, the subject will complete all the assessments planned at this visit, all assessments planned at End of Cycle 1 (if not already performed at the visit) and will enter Cycle 2 Day 1 (which will be on the same day as End of Cycle 1).
- b This visit (Week 36) is the End of Study if the subject is still not eligible for retreatment at the End of Cycle 1.
- c ICF to be signed prior to any screening assessment.
- d To be performed only if this visit is the End of Study or Early Withdrawal.
- e To be assessed at Screening Visit, then 1 week prior to the next planned visit and at the visit. PGI-C will be assessed Week 6 onwards only.
- f To be assessed at the site during the visit.
- g To be assessed at Screening Visit, then 2 weeks prior and 1 week prior to the next planned visit and at the visit.
- h To be assessed at Screening Visit, and then from 2 weeks prior to the next planned visit, subjects need to record daily if they had intercourse, the number of intercourse instances, corresponding pain during each intercourse instance on an 11-point NRS, and details of pain rescue medication if taken to prevent or treat vestibular pain.

Study Procedures and Assessments	Pretreatment		Double-Blind Treatment Period Cycle 1							End of Cycle 1/ EOS or EWD [b]	
	V1	V2	V3	V4	V5 [a]	Additional Visits [a]					
						V6	V7	V8			
Visit Day/Week No.	Screening (Day -14) [m]	Baseline (Day 1)	Week 2 (Day 15)	Week 6 (Day 43)	Week 12 (Day 85)	Week 18 (Day 127)	Week 24 (Day 169)	Week 30 (Day 211)	Week 36 (Day 253)		
Type of visit	Clinic	Clinic	Telephone	Clinic	Clinic	Clinic	Clinic	Clinic	Clinic		
Visit Window	-14 days/ +3 days			±3 days	±5 days	+14 days	±14 days	±14 days	±14 days	±14 days	

i FSH only at Screening Visit.

j Performed after all the other procedures and assessments. Subjects to remain at the clinic for at least 30 minutes after the study drug administration.

k To be assessed weekly from 2 weeks prior to the next planned visit (assessment on the day of the visit should be avoided). Subjects need to rate the level of the corresponding pain following insertion of vaginal dilator (number 6 size) on an 11-point NRS and record details of associated pain medication if consumed.

l Subject interviews on the dilator test to be conducted in Stage 2 by invitation until the target sample of 20 subjects is achieved. Every effort should be made to conduct the interview within 2 weeks of the subject's Cycle 1-Week 6 visit.

m The visit window will be from Day -28 to Day -11.

n To be performed in all subjects in Stage 1 up to 400 U and in a subset of subjects in Stage 2 (i.e. subjects who have never had a vaginal delivery (included attempted vaginal delivery), and at study sites that were provided a perineometer to assess pelvic floor muscle pressure).

\* Study assessments that can be performed remotely if a subject is unable to attend a site visit due to the COVID-19 pandemic, except for the Screening, Baseline and EOS/EWD visits.

\*\* In the event of a remote visit being required, blood sampling should be performed as soon as onsite visit resume and prior to the Week 18 Visit (as much as possible) and recorded as an unscheduled visit.

Table 3 Study Procedures and Assessments – Open-Label Treatment Period

Study Procedures and Assessments	Open-Label Treatment Period Cycles 2 to 4						EOS / EWD
	V9, V13, V17	V10, V14, V18	V11, V15, V19	V12, V16, V20	Additional Visits [b]		
Visit Day/Week No.	Day 1 [a]	Week 2 (Day 15)	Week 6 (Day 43)	Week 12 [b] (Day 85)	Week 18 (Day 127)	Week 24 (Day 169)	Week 48 from Cycle 1 Day 1 (Day 337 from Cycle 1 Day 1) or Early withdrawal
Type of visit	Clinic	Telephone	Clinic	Clinic	Clinic	Clinic	Clinic
Visit Window		±3 days	±5 days	+14 days	±14 days	±14 days	±14 days
Prior/concomitant medication and non-drug therapies (incl. BTX and physiotherapy)*	X [c]	X	X	X	X	X	X
Adverse events*	X [c]	X	X	X	X	X	X
Urine pregnancy test	X [c]						X
Urine test for illicit drugs	X [c]		X				X
Clinical laboratory tests (non-fasting chemistry, haematology)**							X
Blood sample for antibodies**							X
PGI-S [i, j]*	X [d]		X	X	X	X	X
PGI-C [i, j]*	X [d]		X	X	X	X	X
eDiary relationship/partner status [e]*	X [d]		X	X	X	X	X
eDiary dilator insertion [k]*	X [d]		X	X	X	X	X
eDiary intercourse details [f]*	X [d]		X	X	X	X	X
Dilator test	X [d]		X	X	X	X	X
CGI	X [d]		X	X	X	X	X
Study drug administration	X [g]				X [h]	X [h]	X [h]
Assessment for retreatment							

AE=adverse event, BTX=botulinum toxin, CGI=clinical global impression, DRC=data review committee, EOS=end of study, EWD=early withdrawal, ICF=informed consent form, incl.=inclusive, NRS=numeric rating scale, PGI=patient global impression, SF-36=36-item short form survey, V=visit.

- a Day 1 should be done on the same day as last visit of previous cycle. During Stage 1, Day 1 can be delayed until the DRC has confirmed the dose for the next cohort.
- b From Week 12 onwards, if no retreatment is required, the subject will attend Additional Visits every 6 weeks until retreatment is required, or EOS is reached. When subject is eligible and all retreatment criteria all are fulfilled at any visit, the subject will complete the assessments planned at this visit and will enter Day 1 of the next Cycle on the same day and once the DRC has confirmed moving to next cohort for Stage 1.
- c Not to be performed if already done on the same day. AEs are assessed on a continual basis from signing of the ICF.
- d To be performed only if Day 1 is not on the same day as the last visit of previous cycle and the assessment was performed more than 2 weeks prior to Day 1.
- e To be assessed 2 weeks prior and 1 week prior to the next planned visit, and at the visit.

Study Procedures and Assessments	Open-Label Treatment Period Cycles 2 to 4						EOS / EWD
	V9, V13, V17	V10, V14, V18	V11, V15, V19	V12, V16, V20	Additional Visits [b]		
Visit Day/Week No.	Day 1 [a]	Week 2 (Day 15)	Week 6 (Day 43)	Week 12 [b] (Day 85)	Week 18 (Day 127)	Week 24 (Day 169)	Week 48 from Cycle 1 Day 1 (Day 337 from Cycle 1 Day 1) or Early withdrawal
Type of visit	Clinic	Telephone	Clinic	Clinic	Clinic	Clinic	Clinic
Visit Window		±3 days	±5 days	+14 days	±14 days	±14 days	±14 days

f To be recorded daily from 2 weeks prior to the next planned visit. Subjects need to record daily if they had intercourse, the number of intercourse instances, corresponding pain during each intercourse instance on an 11-point NRS and details of pain rescue medication if taken to prevent or treat vestibular pain.

g Performed after all the other procedures and assessments. Subjects to remain at the clinic for at least 30 minutes after the study drug administration.

h No assessment for retreatment if the visit occurs >36 weeks from Cycle 1 Day 1.

i To be assessed only in Cycle 2 (i.e. the first cycle of the open-label treatment period).

j To be assessed 1 week prior to the next planned visit and at the visit.

k To be assessed weekly from 2 weeks prior to the next planned visit (assessment on the day of the visit should be avoided). Subjects need to rate the level of the corresponding pain following insertion of vaginal dilator (number 6 size) on an 11-point NRS and record details of associated pain medication if consumed.

\* Study assessments that can be performed remotely if a subject is unable to attend a site visit due to the COVID-19 pandemic, except for the Screening, Baseline and EOS/EWD visits.

\*\* In the event of a remote visit being required, blood sampling should be performed as soon as onsite visit resume and prior to the Week 18 Visit (as much as possible) and recorded as an unscheduled visit.

The total volume of blood drawn for all evaluations throughout this study is approximately 46 mL for each subject (Table 4).

Table 4 Blood Volume for Collection

Purpose	Maximum Blood Volume per Sample (mL)	Maximum Number of Blood Samples	Maximum Total Blood Volume (mL)
Haematology	3	3	9
Serum Chemistry	4	3	12
FSH	1	1	1
Putative antibodies	12	2	24
Total volume for all tests			46

FSH=follicle stimulating hormone

## 5.2 Study Visits

For the purpose of study visits and procedures, the duration of 1 month=4 weeks=28 days. For assessments done at the Screening Visit, but not repeated at the Baseline Visit, the Screening values will be considered as Baseline.

Subjects are required to remain at the clinic for the required duration of study assessments and for at least 30 minutes after study drug administration.

The priority order for performing the assessments is discussed in Section 6.6.

If the COVID-19 pandemic prevents subjects from coming to the site, study assessments planned in the protocol will be limited to the ones possible remotely, denoted with an asterisk (\*) in Table 2, Table 3, Section 5.2.2, Section 5.2.3 and Section 5.2.4; of note no study assessments should be performed remotely for the Screening, Baseline and EOS/EWD visits. Completion of questionnaires on the subjects' own device will be performed provided that the site staff can access the ePRO system to record the visit date.

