#### **5.2.4 End of Study Visit or Early Withdrawal Visit**

The procedures to be carried out at the EOS Visit or EWD Visit are identical.

The following procedures will be performed at the EOS, or EWD visit (the procedures already performed on the same day at the previous study visit do not need to be repeated):

- mFSFI (pain to be recorded 1 week prior to the visit and at the visit; other domains to be recorded only at the visit; only if the EOS/EWD visit occurs during the double-blind period)
- mVPAQ (pain and life interference to be recorded 1 week prior to the visit and at the visit; other subscales to be recorded only at the visit; only if the EOS/EWD visit occurs during the double-blind period)
- PHQ-9 only if the EOS/EWD visit occurs during the double-blind period
- SF-36 (only if the EOS/EWD visit occurs during the double-blind period)
- PGI-S (to be recorded 1 week prior to the visit and at the visit)
- PGI-C (to be recorded 1 week prior to the visit and at the visit)
- Relationship/partner status (to be recorded weekly from 2 weeks prior to the visit and at the visit)
- Intercourse details (to be recorded daily from 2 weeks prior to the visit)
- Dilator size 6 insertion details (to be recorded weekly from 2 weeks preceding the visit; assessment on the day of the visit should be avoided)

- Urine pregnancy test
- Urine test for illicit drugs
- Blood sampling (nonfasting) for haematology, biochemistry and putative antibodies
- Dilator test
- CGI
- Review of AEs
- New or changed concomitant medications/nondrug therapies.

If the COVID-19 pandemic prevents subjects from coming to the site, EOS visits should be postponed until onsite visits resume.

Subjects who attend the EOS Visit will be considered to have completed the study.

Subjects with ongoing AEs or clinically significant laboratory test abnormalities (as determined by the investigator) will be monitored as described in Section 8.1.5 and Section 8.1.2.4, respectively.

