The psychometric properties of the dilator-induced pain Numeric Rating Scale (NRS), dilator size 6 insertion pain NRS, pain on intercourse NRS, mVPAQ, and modified Female Sexual Function Index (mFSFI) were to be evaluated using data collected from all subjects randomized in Stage 1 and Stage 2. The planned analyses of these data are described in the Psychometric Analysis Plan of validation study D-FR-52120-252. However, these analyses were cancelled following the decision to prematurely terminate the study.

1.3.5 ***Data review Committee and planned Analyses***

Data Review Committee

A DRC has been established to make recommendations for dose escalation and dose de-escalation or study termination decisions in Stage 1. It was planned that (a) if no subject reports a clinically significant AE (defined in the protocol section 3.1.1.1) in a cohort, the DRC will meet once all PVD2 and PVD1 evaluable subjects of a dose level have reached Week 6 to review the unblinded efficacy and safety data and decide the dose for the next cohort or proceed to Stage 2; (b) If any subject reports a clinically significant AE, then further enrolment into the cohort as well as retreatment in open label cycles at the current dose will be suspended and an ad hoc DRC meeting will be scheduled to review the data and make a recommendation with regards to further conduct of the cohort and of Stage 1.

Details related to DRC membership, responsibilities, procedures, role and remit are described in the DRC charter.

Early Study Termination Decision

Following the DRC meeting organized to review safety and efficacy data of cohorts 1 to 6 on the 16 OCT 2020, the DRC sent the following recommendation:

"No safety concerns noted in review of all available data. Efficacy cannot be assessed due to the small sample size of cohorts. The DRC would recommend that Stage 1 is not used to make an efficacy assessment, therefore there is no justification to increase the dose, nor to move to Stage 2."

Ipsen subsequently decided to close the study early and to run the final analysis based on available Stage 1 data. Subjects in the study are followed until 12 weeks after the last dose as described in the protocol section 3.9.

Final Analysis

The final analysis will be carried out once all subjects from cohorts 1 to 6 have completed end of study evaluation, after the database lock. All unblinded safety and efficacy data available at the time of the database lock will be analysed.

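### The COVID-19 rule bars all remote assessment at early-withdrawal visits and gives them no fallback, so a subject who withdraws and cannot attend has no protocol-defined final safety review

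*Protocol*

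**What the plan says.** The rules for subjects who cannot come to the site were added in protocol Version 6.0 (Appendix 10).

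- **5.1** lets the investigator hold a telemedicine visit and contact the subject's general practitioner, so that safety events since the previous visit are captured. Its text makes no exception for any visit type.
- **5.2** limits remote work to items "denoted with an asterisk (\*) in Table 2, Table 3, Section 5.2.2, Section 5.2.3 and Section 5.2.4", and then adds: "of note no study assessments should be performed remotely for the Screening, Baseline and EOS/EWD visits".
- **Tables 2 and 3** star the adverse-event and concomitant-medication rows and most patient-reported items. The footnote to each table allows these remotely "except for the Screening, Baseline and EOS/EWD visits".
- **5.2.4** says of content: "The procedures to be carried out at the EOS Visit or EWD Visit are identical". For the pandemic it says only that "EOS visits should be postponed until onsite visits resume". It is silent on EWD.
- **4.4**, on withdrawal after dosing, says: "A complete assessment should be made and final evaluations be done at the time of" the withdrawal, and refers to 5.2.4 for what to do.
- **SAP 1.3.5**, after the early closure, says: "Subjects in the study are followed until 12 weeks after the last dose as described in the protocol section 3.9".

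**The concern.** Safety from Baseline to Cycle 1-Week 6 is the Stage 1 primary endpoint (3.2.1), and the SAP's final analysis takes all safety data available at lock. The EWD visit is the last planned occasion on which a departing subject is asked about adverse events. Asking is something the protocol already does by telephone: the Week 2 contact is always a call, and the starred reviews may be remote at Week 6, Week 12 and later visits. Barring the same question at the EWD visit, with nothing in its place, gives up information that one call could obtain. In cohorts of 8 to 10 subjects a single missed event matters.

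A site would also receive conflicting instructions: 5.1 and 4.4 point towards collecting the data, while 5.2 and the footnotes forbid it.

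**Working it through.** No stated figure needs reproducing. The check is a comparison of the provisions.

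**1. What the prohibition covers.** The adverse-event and concomitant-medication rows carry the asterisk and are scheduled at EOS/EWD in both tables. The footnote exception therefore removes them at that visit, and 5.2 says the same in general terms.

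**2. What replaces the visit.**

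| Visit, subject cannot attend | Remote adverse-event review | Stated alternative |
|---|---|---|
| Week 2 | Always by telephone | Not needed |
| Week 6, Week 12, additional visits | Allowed (starred) | Not needed |
| EOS | Barred | Postpone until on-site visits resume |
| EWD | Barred | None |

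**3. Where the provisions disagree.**

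- 5.1 offers telemedicine without excluding EWD; 5.2 and the footnotes exclude it.
- 4.4 requires the 5.2.4 assessments at the time of withdrawal; 5.2 makes that impossible for a subject who cannot travel.
- 5.2 names 5.2.4 among the sections with starred items, but no item in the 5.2.4 list has an asterisk.
- The double-asterisk note on deferred blood sampling applies when a visit is remote. It is attached to the antibody row, whose samples fall only at Screening and EOS/EWD (Tables 2 to 4), and neither of those visits may be remote.

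**4. What continues without the visit.** Adverse events are monitored from consent to end of study through questioning or spontaneous report (8.1). They are described as continually assessed (Table 3, footnote c). Persisting events are followed after discontinuation (8.1.5). SAEs are reported within 24 hours of the investigator's knowledge, and suspected related events are reported even after completion (8.1.6). If an adverse event or laboratory abnormality is the reason for leaving, monitoring continues and the event is recorded (4.4).

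These routes cover events that are volunteered or already known. Routine active questioning is tied to visits (8.1.5), and the EWD visit is the one blocked.

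**5. Length of the unreviewed stretch.** Nominal Cycle 1 contacts are Days 1, 15, 43 and 85, then every 6 weeks:

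- 15 - 1 = 14 days
- 43 - 15 = 28 days
- 85 - 43 = 42 days, and 42 days thereafter

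If every earlier contact took place, on site or remotely, the stretch without active review is at most one of these intervals, before visit windows.

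**6. Use in the analysis.** SAP 3.1.3 reassigns a withdrawal visit to the next empty visit; without an EWD visit there is nothing to reassign. SAP 3.9.6 plans an antibody shift table from baseline to EOS/EW; a subject without that sample has no post-treatment antibody result. SAP 3.15 summarises withdrawals due to COVID-19, so the plan expects such subjects.

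**The case against.** The strongest reply is that adverse-event collection does not depend on the EWD visit. Sections 4.4, 8.1, 8.1.5 and 8.1.6 keep reporting and follow-up open, 5.1 can be read as allowing a telemedicine contact, and 4.4 asks for all efforts to complete observations. This stands to the extent that safety information does not cease. It does not remove the gap: a site that follows the specific prohibition in 5.2 over the general wording elsewhere would reasonably not make the call.

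Postponing EOS is also defensible. It keeps collection open and preserves the laboratory and antibody samples. The documents neither provide for nor rule out contact in the meantime.

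Three stronger readings are tempting and are not supported:

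- **That such a subject gives no final safety data.** The continuing duties in 4.4 and 8.1 to 8.1.6 contradict this.
- **That two-thirds of the primary safety window is lost.** Withdrawal just before Week 6, after a last contact on Day 15, would leave 28 of 42 days (28/42 = 67%) without active review. That is a theoretical worst case. The rule is dated 08 October 2020, and the Data Review Committee (DRC) reviewed Cohorts 1 to 6 on 16 October 2020 (SAP 1.3.5), 8 days later. If that was the scheduled review under 3.1.1.2, evaluable subjects had already passed Week 6.
- **That the highest dose is made to look safer.** The planned 500 U share of Dysport subjects in Cohorts 1 to 6 is 16 of 46 (8+8+8+6+8+8 = 46; 16/46 = 35%). That is an allocation, not a measure of loss. Follow-up during the pandemic is not the same as follow-up under this rule, and subjects from earlier cohorts could also still be in open-label cycles.

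**Conclusion.** The concern holds as a conflict between provisions with a practical consequence: a subject who withdraws and cannot attend has no protocol-defined final safety review. This is an express prohibition, not a missing detail, and only EOS has a fallback.

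The size is modest and cannot be fixed from the documents. For each affected subject it is the active review of at most one interval between contacts, plus the on-site tests. The number affected is not given. After the closure decision, the exposure lies mainly in later visits during the remaining follow-up.

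The conclusion assumes that sites apply 5.2 literally and that a subject who has withdrawn does not return for a later visit, which the protocol does not offer. The separate remote-assessment guidance mentioned in 5.1 is not among the documents; it may help sites in practice but would not remove the contradiction in the protocol.

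**What to change.** Reconcile 5.1, 5.2, 5.2.4, 4.4 and the asterisk footnotes of Tables 2 and 3:

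- At an EWD visit that cannot be held on site, allow the starred items (adverse events, concomitant medication, electronic patient-reported questionnaires) by telephone or on the subject's own device.
- Put the asterisks on those items in 5.2.4, so that the reference in 5.2 is correct.
- Keep laboratory, antibody and dilator tests on site, and clarify the double-asterisk note on the antibody row, which cannot operate as written.
- Optionally, add a telephone adverse-event review on the planned date of a postponed EOS visit.

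The cost is protocol wording and one call per affected subject, using a procedure that already exists. The downside is that these EWD visits are partial: the antibody result and the other on-site tests would still be missing for that subject.
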